9.1. Adverse Events

The primary variable for evaluation of the safety profile will be the number and percentage of AEs recorded after study drug administration. For selected of AE tables, additional summaries based on reporting period of adverse events following each vaccination (RabAvert® or Rabipur®) will also be presented.

The collection periods for adverse events are:

- Solicited AEs: Through Study Day 8
- Unsolicited AEs: (After Study Day 8) Through Study Day 43
- SAEs: Entire study period (i.e., 365 days)

All AEs will be classified by SOC and PT according to MedDRA, Version 21.0 or later. Summaries of the total number of treatment-emergent AEs (TEAEs) and the number and percentage of subjects with at least one TEAE will be provided by treatment. TEAEs will be presented by SOC and PT. At each level of subject summarization, a subject is counted once if the subject reported one or more events. Percentages will be calculated out of the number of subjects in the As-treated Population.

The summary of TEAEs will be presented in alphabetical order of SOC. Within each SOC, PTs will be sorted in descending order from the PT with the highest total frequency (that is, summed across all treatment groups) to the PT with the lowest total frequency. If the total frequency for any two or more PTs is equal, the PTs will be presented in alphabetical order.

SAEs will be recorded through the final study visit for all subjects. Listings will be provided for subjects with SAEs. Listings will also be provided for subjects who have discontinued prematurely due to an AE.

All AE summaries will be restricted to TEAEs only. A TEAE is defined as any event not present before exposure to study drug or any event already present that worsens in either intensity or frequency after exposure to study drug.

For inclusion in TEAE tables, incomplete AE start and end dates will be imputed following rules specified in Section 15.3.1.

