9.1.2. Unsolicited Adverse Events

An overview summary of the number and percentage of subjects with any unsolicited TEAE, unsolicited serious TEAE, unsolicited treatment-related TEAE, unsolicited treatment-related serious TEAE, unsolicited TEAE leading to study drug discontinuation, unsolicited TEAE leading to study discontinuation, and unsolicited AE leading to death will be provided by treatment group.

All unsolicited AEs will be presented in a listing.

Summary of unsolicited TEAEs will also be repeated for the following:

- Serious Adverse Events;
- Treatment-Related Adverse Events;
- Treatment-Related Serious Adverse Events;
- Adverse Events Leading to Study Discontinuation.

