Immunogenicity will be summarized for initial LRG subjects, general LRG subjects and NRG subjects, separately. The summary will take forms of GMC or GMT and be based on standard log transformations (Section 15.2) for all time points as collected and as available. If the assay read-out does not occur at the starting dilution – indicating a very low amount of antibodies, below the detection limit of the assay – then the antibody titer for the sample is set to D/2, half of the starting dilution. No imputation for missing data will be performed. Data will be transformed as appropriate prior to analysis. GM, Geo SD and 95% CI will be provided in summary tables. Inferential testing will not be performed. In case of pre-vaccination immunogenicity levels are not zero, GM fold increase will be presented as the alternative statistics to GMC or GMT. Let v_{pre} be a subject's pre-vaccination (baseline) immunogenicity value and v_{post} be the post-vaccination value, then the fold increase is

$$f_i = v_{post}/v_{pre}.$$

Fold increases express intra-individual relative increases in immunogenicity values. Just like immunogenicity values, log transformed fold increases tend to be normally distributed, and for the statistical analysis of fold increases the methods described for the analysis of immunogenicity values can be used.

13. Interim Analysis

Not applicable. Regarding summaries planned for DSMB meetings, please refer to a standalone DSMB Charter.

14. Changes in the Planned Analysis

Not applicable in this version.

15. Appendices

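### SAP 9.1 opens the unsolicited adverse event period only after Study Day 8, so early events off the solicited list can drop out of the unsolicited safety outputs

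*SAP*

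**What the plan says.** SAP 9.1 introduces its three windows with "The collection periods for adverse events are". Solicited AEs run through Study Day 8, SAEs run for the whole 365 days, and the third window is "Unsolicited AEs: (After Study Day 8) Through Study Day 43". The same section promises a pooled table ("TEAEs will be presented by SOC and PT") and, for selected tables, "additional summaries based on reporting period of adverse events following each vaccination".

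SAP 9.1.1 limits solicited events to 11 named non-local symptoms. It explains that local findings are not solicited because the bite and its care confound them.

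SAP 9.1.2 then builds a set of outputs on the unsolicited category:

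- an overview: "An overview summary of the number and percentage of subjects with any unsolicited TEAE, unsolicited serious TEAE, unsolicited treatment-related TEAE", and further rows;
- a listing: "All unsolicited AEs will be presented in a listing";
- repeats: "Summary of unsolicited TEAEs will also be repeated for the following", naming serious, treatment-related, treatment-related serious, and events leading to study discontinuation.

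The section does not say what makes an event unsolicited. SAP section 14, on changes to the planned analysis, reads "Not applicable in this version".

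**The concern.** The protocol has no delayed start for unsolicited events, and the SAP declares no departure from it. Because 9.1.2 gives no definition, the 9.1 bullet is the only text that bounds the category. Anyone programming from it would open the unsolicited tables on Day 9.

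Days 1-8 are the period in which acute reactions to the study treatment would be expected to show. They contain the single Study Drug administration. Protocol 1.4 names local injection-site manifestations as the second most common related event in earlier SYN023 studies, although those were not in animal-exposed subjects (Protocol 3.9.3). Local findings are deliberately left off the solicited list, so on those days the unsolicited category is the only one that can hold them.

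Vital-sign abnormalities raise the same problem. Protocol 7.7.1 has them reported as AEs, and scheduled vital signs are taken only on Days 1, 4 and 8. Apart from fever, they are not on the solicited list. By-arm unsolicited tables that begin on Day 9 would under-report early events of all these kinds.

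**Working it through.** No power or sample size calculation is involved. The check compares the texts and counts the outputs and visits affected.

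**Step 1. The windows side by side.**

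| Source | Unsolicited or ordinary AEs | Solicited AEs |
|---|---|---|
| Protocol 3.12.1 | Through Day 43, no later start given | Through Day 8 |
| Protocol 7.7.1 | All post-vaccination time points | All post-vaccination time points |
| Protocol Tables 3-1 and 3-2 | AE row on Days 1, 4, 8, 15, 29, 43 | Separate row on Days 1, 4, 8 |
| SAP 15.1.1, notes g and h; SAP 15.1.2, note f | AEs on Days 1, 4, 8 | Solicited AEs on the same days |
| SAP 15.1.1, note l | Same AE category on Days 15, 29, 43 | None |
| SAP 9.1 | After Day 8 through Day 43 | Through Day 8 |

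Only SAP 9.1 has the two windows running one after the other. Every other source has them overlapping on Days 1-8. If the bullet is a collection period, as its heading says, it contradicts the SAP's own schedules.

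**Step 2. Where an early off-list event goes.** Take an injection-site reaction on Day 3. It is not among the 11 symptoms, so it is not solicited. It precedes the SAP 9.1 window, so it is not unsolicited. It has no category.

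**Step 3. Outputs affected on that reading.**

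- SAP 9.1.2: overview 1 + listing 1 + repeats 4 = 6. The overview has 7 rows, all labelled unsolicited: any, serious, treatment-related, treatment-related serious, leading to drug discontinuation, leading to study discontinuation, leading to death. The word for repetition also implies a base unsolicited summary, which is not counted here, so 6 is a minimum.
- SAP 9.1.3 (relationship) and 9.1.4 (severity): 2 more, but only if those tables are assembled from the two categories rather than from all TEAEs.

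**Step 4. Share of the schedule excluded.**

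- Days: 8 / 43 = 18.6%, leaving Days 9-43, that is 43 − 8 = 35 days.
- Scheduled AE visits (Days 1, 4, 8, 15, 29, 43): 3 / 6 = 50%.
- Injection-site examinations (Days 1, 4, 8, 15, 29): 3 / 5 = 60%.
- Vaccination periods: those from the Day 1 dose to the Day 4 dose and from the Day 4 dose to the Day 8 dose lie wholly inside Days 1-8. If an unsolicited table is among those split by vaccination period, 2 of 5 periods would show no unsolicited events (2 of 4 for subjects on the four-dose schedule).

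The documents give no onset data, so none of these shares can be turned into a number of events.

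**Step 5. What is not affected.** The events are still recorded at the visits. The pooled TEAE summary by SOC and PT in SAP 9.1 is not split by category. SAEs, AE discontinuations and deaths have their own listings, and 9.1.3 and 9.1.4 have separate SAE tables.

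**The case against.** The strongest reply is that no narrowing was meant. SAP 9.1 opens by counting all AEs after study drug administration, its TEAE definition has no delayed start, the schedules collect AEs from Day 1, and section 14 declares no change. On that view the parenthesis only marks the point after which a listed symptom counts as unsolicited. This may well have been the intent. The bullet does not say so, however: it qualifies the whole unsolicited category. Two programmers could follow the SAP faithfully and produce different tables.

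A second reply is that a collection period is not a category definition. If it were, its Day 43 end would also remove later SAEs and deaths from the unsolicited serious and death rows, which is implausible when SAEs are collected for 365 days. That is a fair argument against the literal reading as intent. It also shows that 9.1.2 needs a definition of its own.

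A third reply is that little is lost, because the pooled TEAE tables and the separate listings survive, and the phrase covering solicited and unsolicited TEAEs in 9.1.3 and 9.1.4 most naturally means all TEAEs. This stands as a limit on the impact. It does not restore the 9.1.2 outputs: the unsolicited treatment-related row and its repeat would still begin on Day 9.

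**Conclusion.** The SAP bullet is wrong as written. It conflicts with Protocol 3.12.1 and 7.7.1 and with the SAP's own schedules, and the conflict is not declared. If followed literally, it removes off-list events on Days 1-8 from at least 6 named unsolicited outputs, and from 2 more if the relationship and severity tables are built from the two categories. Confidence in the textual conflict is high. The tabulation consequence assumes that the bullet is programmed as it reads, and its size in events is unknown.

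The point concerns how early safety events are classified and tabulated. Data collection, the pooled safety summary and the efficacy endpoints are untouched. It should be corrected, because the affected days are those around dosing and the correction is small.

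**What to change.** Three changes to the SAP:

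1. In 9.1, replace the bullet with: *Unsolicited AEs: from Study Drug administration through Study Day 43.*
2. In 9.1.2, add: *An unsolicited AE is any AE not on the solicited list, or a listed symptom with onset after Study Day 8.* Apply this to the overview, the listing and all four repeats. The definition carries no end day, so SAEs collected to Day 365 remain in the serious and death rows.
3. In 9.1.3 and 9.1.4, state that the TEAE relationship and severity tables cover all TEAEs.

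The cost is one bullet, one definition sentence and two clarifying phrases, with the 9.1.2 outputs programmed to the definition before database lock. The CRF, data collection and sample size do not change.

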9.1.1. Solicited Adverse Events

Local study drug injection will be made in the immediate area of an animal bite. Since the trauma and wound management will create confounding local findings they will not be solicited in this trial. The reporting period during which solicited adverse events will be evaluated is through Study Day 8. The non-local symptoms that will be solicited include:

headache, arthralgia, myalgia, rash, pruritus, urticaria, dyspnea, chest pain, cough, fever, and chills.

Summary of solicited TEAEs will be provided. All solicited AEs will be presented in a listing.

9.1.2. Unsolicited Adverse Events

An overview summary of the number and percentage of subjects with any unsolicited TEAE, unsolicited serious TEAE, unsolicited treatment-related TEAE, unsolicited treatment-related serious TEAE, unsolicited TEAE leading to study drug discontinuation, unsolicited TEAE leading to study discontinuation, and unsolicited AE leading to death will be provided by treatment group.

All unsolicited AEs will be presented in a listing.

Summary of unsolicited TEAEs will also be repeated for the following:

- Serious Adverse Events;
- Treatment-Related Adverse Events;
- Treatment-Related Serious Adverse Events;
- Adverse Events Leading to Study Discontinuation.

9.1.3. Relationship of Adverse Events to Study Drug

Summary of TEAEs (solicited/unsolicited) by relationship to study drug will be presented. The investigator will provide an assessment of the relationship of the event to the study drug. The greatest degree of causal relationship (definite > probable > possible > unlikely related > not related) determined by either the investigator or local medical monitor after their discussions will determine the ultimate classification of the adverse event. Definite, probable and possible are considered related. Not related and unlikely related are considered unrelated.

In the TEAE relationship table, if a subject reports multiple occurrence of the same TEAE, only the most closely related occurrence will be presented. Treatment-emergent AEs that are missing a relationship will be presented in the summary table as “Related” but will be presented in the data listing with a missing relationship.

Treatment-emergent SAEs by relationship to study drug will also be presented in a table. Treatment-emergent SAEs that are missing a relationship will be presented in the table as “Related” but will be presented in the data listing with a missing relationship.

9.1.4. Severity of Adverse Event

Summaries of TEAEs (solicited/unsolicited) by severity will be presented. The severity that will be presented represents the most extreme severity captured on the CRF page. The possible severities are “Mild”, “Moderate”, and “Severe”.

In the TEAE severity table, if a subject reported multiple occurrences of the same TEAE, only the most severe will be presented. An additional row “Missing” must be added for the missing severity.

Treatment-emergent SAEs by severity will also be presented in a table.

9.1.5. Death

All subjects who have an AE with an outcome of death will be presented in a listing.

9.2. Clinical Laboratory Evaluations

All clinical laboratory test results will be presented in listings.

Clinical laboratory evaluations include hematology, serum chemistry, coagulation and urinalysis assessments. Summaries will be based on the As-treated Population.

Unscheduled assessment results will be listed and considered when deriving by-subject maximum and minimum values; however, these will not be included in the by-time-point summary tables. An average value will be derived for repeating assessment values taken on the same day for the by-time-point summary tables.

Observed and change from baseline values at each study visit with by-subject post-baseline maximum and minimum values among all visits will be summarized for numeric test results. Frequency summaries (number of subjects and percentages) will be provided for categorical tests. The number of subjects (n) with a non-missing result at each time point will be presented by treatment group and overall.

Shift summaries for baseline to post-baseline new abnormality (normal to \geq grade 1 or increase in toxicity grade) will be provided at each post-baseline time point for tests (Protocol Appendix B). For tests with available normal ranges, shift summaries for baseline to post-baseline new abnormality (normal to low, normal to high, low to high and high to low) will be provided at each post-baseline time point. By-subject maximum and minimum values (with unscheduled values considered) will be used to produce an overall shift for tests with at least one post-baseline assessment.

When available, clinical significance (normal, abnormal but not clinically significant, or abnormal and clinically significant) and shifts from baseline to post-baseline will be provided at each post-baseline time point.

For shift summaries, the number of subjects with at least one non-missing post-baseline assessments will be presented. Percentages will be calculated based on the number of subjects. At each level of anomalies (low or high; abnormal but not clinically significant, or abnormal and clinically significant), a subject is counted once if he/she reports multiple anomalies at that level. However, a subject might appear multiple times if he/she reports anomalies at multiple levels.

Clinical laboratory being reported as adverse events will only be included in the summary of adverse events.

9.3. Vital Sign Measurements

Summaries for vital signs results on the As-treated Population including change from baseline and will be provided following the same presentation for numeric clinical laboratory tests. Shift summaries for baseline to post-baseline new abnormality (normal to \geq grade 1 or increase in

toxicity grade) will be provided at each post-baseline time point for tests (Protocol Appendix B). By-subject maximum and minimum values (with unscheduled values considered) will be used to produce an overall shift for tests with at least one post-baseline assessment.

9.4. Physical Examination

Summaries for physical exam results on the As-treated Population including shifts will be provided following the same presentation for categorical clinical laboratory tests.

10. Pharmacokinetics

To describe the pharmacokinetics of SYN023 using non-compartmental analysis, V_d , C_{max} , T_{max} , AUC_{1-t} , AUC_{1-inf} , $t_{1/2}$, Cl , and λ_z will be calculated, when possible, in the LRG and NRG Per-protocol and As-treated Populations.

10.1. Handling Missing Data

Concentrations that are below the limit of quantification (BLQ) will be treated as zero for descriptive statistics. Mean BLQ concentrations will be presented as BLQ, and the SD and coefficient of variation (CV) will be reported as not applicable. Missing concentrations will be excluded from the calculation.

10.2. Pharmacokinetic Concentrations

Blood samples will be obtained during the course of the study for use in determining the PK concentrations of CTB011 and CTB012 in serum. These will be collected before administration of study drug on Study Day 1 for all subjects, then on Study Days 4, 8, 15, 29, 43, 71, 127, 155, 183 and 274 for the LRG; and on Study Days 4, 8, 15 and 99 for the NRG.

Individual serum concentrations of CTB011 and CTB012 will be presented in the data listings and summarized by nominal time point for ease of presentation using descriptive statistics (n , mean, SD, CV, min, median, and max), by ADA status, and also by Per-protocol (LRG and NRG) and As-treated Populations. The mean serum concentrations of CTB011 and CTB012 will be plotted versus nominal collection time, and the individual serum concentration of CTB011 and CTB012 will be plotted versus actual collection time on both linear and semilogarithmic scales, by ADA status.

10.3. Pharmacokinetic Parameters

The serum concentration-time data for CTB011 and CTB012 will be analyzed by non-compartmental analysis using WinNonlin Phoenix Version 8.0 or higher. For PK analysis, actual sampling times and actual doses administered will be used. For the calculation of PK parameters, all serum concentrations that are BLQ prior to the first measurable concentration will be set to zero. The BLQ values that are between measurable concentrations will be set to missing. The BLQ values that occur at the end of the profile after the last quantifiable concentration will be set to missing.

If data allow, the following PK parameters will be derived from the individual serum concentrations of CTB011 and CTB012 over time profile using non-compartmental methods:

AUC _{1-t}	Area under the serum concentration-time curve from time 0 on Study Day 1 to the last quantifiable concentration, calculated using the linear trapezoidal linear interpolation rule
AUC _{1-inf}	Area under the serum concentration-time curve from time 0 on Study Day 1 extrapolated to infinity, calculated using the formula: AUC _{1-inf} = AUC _{1-t} + [C _t / λ _z], where C _t is the last measurable serum concentration and λ _z is the terminal elimination rate constant. If the extrapolated area (C _t /λ _z) is greater than 20% of AUC _{1-inf} , then AUC _{1-inf} and its associated parameters (CL/F and Vd/F) will be set to missing.
C _{max}	Maximum observed serum concentration
T _{max}	Time of maximum observed serum concentration
λ _z	Terminal elimination rate constant, where λ _z is the magnitude of the slope of the linear regression of the log concentration versus time profile during the terminal phase. λ _z will only be retained if R ² ≥ 0.80 and 3 points in the terminal phase that do not include C _{max} are included in determining the regression line.
t _{1/2}	Terminal half-life (whenever possible), calculated as ln(2)/λ _z
CL/F	Apparent clearance, calculated as Dose/AUC _{1-inf}
Vd/F	Apparent volume of distribution, calculated as (CL/F)/λ _z

Individual serum PK parameters of CTB011 and CTB012 will be presented in the data listings. Further, CTB011 and CTB012 PK parameters will be summarized using descriptive statistics (n, mean, SD, CV, min, median, and max) by ADA status, and also by Per-protocol (LRG and NRG) and As-treated Populations.

11. Pharmacodynamics

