The second element of the endpoint is noninferiority of the Study Day 99 GMC of RVNA in SYN023 recipients compared to Study Day 99 GMC of RVNA in the HRIG recipients. It is important that any immunoglobulin product administered be compatible with rabies vaccination and thus not significantly inhibit the immune response to rabies vaccination. When should this comparison of immunogenicity be performed and secondly what margin of non-inferiority should be employed? It is Synermore's position that assessment of rabies vaccine immunogenicity should be performed on or around Study Day 99. This interval is over four times the half-lives of administered human IgG. By Study Day 99 anti-rabies antibodies including SYN023 that were administered for prophylaxis will have dissipated. Thus Study Day 99 RVNA values will reflect the long term production of natural rabies antibodies from vaccination. Synermore defines non-inferiority of a rabies vaccine response with a 20% margin of non-inferiority and equal number of SYN023 and HRIG subjects in HRIG (Section 7.8.2). The alpha value is taken to be ≤ 0.025 .

The third element is the percentage of PEP recipients that have a serum RVNA concentration ≥ 0.5 IU/mL on Study Day 99. This is the RVNA concentration that is generally recognized to reflect protection from rabies when subjects are vaccinated. Achievement of RVNA ≥ 0.5 IU/mL should indicate that the subject's vaccination has elicited a protective immune response despite the geometric mean concentration, thus any differences are not clinically important. Synermore defines non-inferiority of the percentage of SYN023 subjects with serum RVNA concentration ≥ 0.5 IU/mL, with a 20% margin of non-inferiority and equal number of SYN023 and HRIG subjects in HRIG (7.8.3). The alpha value is taken to be ≤ 0.025 .

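### In NRG subjects still quantifiable on Day 99, the SAP's linear trapezoidal rule draws one straight line from Day 15 to Day 99, overstating SYN023 AUC1-t by about 27-35% and, where CL/F can be reported, understating it by about 20-25%

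*SAP*

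**What the plan says.** SAP 10.3 derives AUC1-t for CTB011 and CTB012 from time 0 on Study Day 1 "to the last quantifiable concentration, calculated using the linear trapezoidal linear interpolation rule". It gives no separate rule for falling concentrations.

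After the pre-dose sample, SAP 10.2 schedules pharmacokinetic samples "on Study Days 4, 8, 15 and 99 for the NRG". SAP 15.1.2 and Protocol Appendix D also place an NRG sample on Day 99.

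The remaining rules in SAP 10.3 that matter here are:
- AUC1-inf is AUC1-t plus the last concentration divided by lambda-z. CL/F is "Apparent clearance, calculated as Dose/AUC" to infinity.
- Lambda-z is kept only if R² is at least 0.80 and there are "3 points in the terminal phase that do not include" Cmax.
- AUC1-inf, CL/F and Vd/F are set to missing if the extrapolated area "is greater than 20% of AUC" to infinity.
- On trailing values below the limit of quantification (BLQ): "The BLQ values that occur at the end of the profile after the last quantifiable concentration will be set to missing".

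On elimination, Protocol 1.6 says of Day 99: "This interval is over four times the half-lives of administered human IgG". Its rationale for pregnancy avoidance adds that SYN023 is undetectable by Day 99 and that Day 121 lies more than five half-lives after dosing. Protocol 1.1 gives about 21 days as the half-life of rabies immune globulin, the only numerical half-life in the documents.

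**The concern.** A straight line between two points on an exponential decline lies above the curve. Over one or two weeks the error is small; over 84 days it is not. The inflated area passes directly into AUC1-t, AUC1-inf and CL/F, and through CL/F into Vd/F.

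Describing SYN023 pharmacokinetics in the LRG and NRG is a secondary objective, and SAP 10.3 summarises the parameters by population and by ADA status. Because the LRG is sampled more densely, the rule distorts the two risk groups unequally. An apparent LRG-NRG difference in clearance could come from the integration alone. Whether a subject's area ends on Day 15 or Day 99 also depends on which side of the assay limit the last sample falls. An ADA effect on elimination could influence that, so ADA status and the length of the integrated interval may become mixed.

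**Working it through.** The documents state no AUC, CL/F or bias figure, so there is nothing to reproduce. The size below comes from a model.

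**Inputs**
- NRG times after dosing: 0, 3, 7, 14 and 98 days (Study Days 1, 4, 8, 15, 99; SAP 10.2).
- Half-life: 21 days (Protocol 1.1, for rabies immune globulin). Upper bounds are 120/5 = 24 days (Day 121 is over five half-lives) and 98/4 = 24.5 days (Day 99 is over four). At 21 days, 98/21 = 4.7 and 120/21 = 5.7, which agrees with both statements.
- Assumptions not in the documents: one compartment, first-order absorption with a half-life of 0.5-1 day, and a 14-day half-life as a sensitivity case.

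**The Day 15-99 segment alone**, with the Day 15 level set to 1 and k = 0.693/half-life:
- 21 days: the Day 99 level is 2^(-84/21) = 0.0625. Linear area 84 × (1 + 0.0625)/2 = 44.6; exact area (1 - 0.0625)/0.0330 = 28.4; ratio 1.57.
- 24 days: ratio 1.45. 14 days: ratio 2.15.

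**Whole profile**, C(t) = ka/(ka - k) × [exp(-kt) - exp(-ka t)], half-life 21 days, absorption half-life 0.5 day:
- Relative concentrations: 0, 0.912, 0.813, 0.645, 0.0403.
- Linear AUC1-t = 1.37 + 3.45 + 5.10 + 28.80 = 38.72. The exact area to Day 99 is 29.08, so the error is 38.72/29.08 - 1 = +33%.
- Lambda-z from Days 8, 15 and 99 is 0.0330. AUC1-inf = 38.72 + 0.0403/0.0330 = 39.94, against a true 30.30. CL/F error = 30.30/39.94 - 1 = -24%.
- Extrapolated share = 1.22/39.94 = 3.1%, far below 20%, so the SAP's extrapolation check does not catch the error.

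**Range**

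| Half-life, absorption half-life | Sampled Cmax | AUC1-t, linear | CL/F, linear | AUC1-t, linear-up/log-down |
|---|---|---|---|---|
| 24 d, 0.5 d | Day 4 | +27.1% | -20.3% | -2.6% |
| 24 d, 1 d | Day 8 | +28.7% | missing | -1.7% |
| 21 d, 0.5 d | Day 4 | +33.2% | -24.1% | -2.9% |
| 21 d, 1 d | Day 8 | +35.1% | missing | -1.9% |
| 14 d, 0.5 d (assumed) | Day 4 | +55% | -35% | -4% |
| 14 d, 1 d (assumed) | Day 4 | +58.6% | -36.8% | -3% |

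Where the sampled Cmax falls on Day 8, only Days 15 and 99 remain. Lambda-z then fails the three-point rule and CL/F is missing. AUC1-t is still reported and still inflated.

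**Day 99 BLQ.** AUC1-t ends on Day 15. The post-dose samples left are Days 4, 8 and 15, and one of them is Cmax. At most two points remain, so lambda-z, AUC1-inf, CL/F and Vd/F are missing. Every NRG CL/F that the SAP can report therefore comes from a subject whose area includes the 84-day line.

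**Truncation, considered separately.** Two similar subjects either side of the assay limit, half-lives 14-24 days, have a Day 99 area divided by Day 15 area of 3.5- to 4.2-fold with the linear rule, 2.2- to 3.2-fold with linear-up/log-down, and 2.1- to 3.1-fold with exact integrals. Most of the gap is truncation.

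**LRG.** Protocol Table 3-1 samples Days 4, 8, 15, 29, 43 and 99, and the linear error is about +3% to +6%. SAP 10.2 instead lists Days 71, 127, 155, 183 and 274 after Day 43, with no Day 99, and the error is about +1% to +3%.

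**The case against.** The strongest reply is that the affected group may be empty. The protocol expects SYN023 to be undetectable by Day 99. If so, the line is never drawn, AUC1-t stops at Day 15, CL/F is not produced, and SAP 10.3 allows for this by deriving parameters only if the data allow. This stands as a limit on scope: no quantification limit is given, so the number affected cannot be estimated. It does not remove the point. The Day 99 sample is scheduled, and in the model about 4-7% of the sampled peak remains on Day 99 at half-lives of 21-24 days.

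A reader might infer three stronger things that the documents do not support.
- *All NRG exposure and clearance values are biased, so the NRG will appear to clear SYN023 more slowly.* The bias arises only where Day 99 is quantifiable, and some of those subjects will have no CL/F.
- *The error reaches 59% in AUC1-t and 37% in CL/F.* Those figures need a 14-day half-life, which appears nowhere in the documents. At 14 days only about 1% of the sampled peak remains on Day 99, so subjects who are quantifiable then are more likely slow eliminators. At 28 days the AUC1-t error is about +21% to +22%.
- *The roughly fourfold gap between subjects either side of the assay limit is caused by the linear rule.* Most of it is truncation and would remain under any rule.

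Two further caveats are fair. The good performance of log-down integration was checked only on the mono-exponential decline that it assumes, not on ADA-altered profiles. And the pharmacokinetic results are descriptive, with individual concentrations listed, so the areas could be recomputed later.

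**Conclusion.** The point holds, conditionally. For NRG subjects quantifiable on Day 99, the prescribed rule overstates AUC1-t by about 27-35% at half-lives of 21-24 days. It understates CL/F by about 20-25% where sampled Cmax is on Day 4 and lambda-z is kept. An assumed 14-day half-life would raise these to about 55-59% and 35-37%. The sizes rest on one-compartment kinetics, an assumed absorption half-life of 0.5-1 day, and a half-life documented for immune globulin and only bounded for SYN023. The direction does not depend on these exact values: it follows from a straight line across a convex decline.

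How many subjects are affected is unknown. The 2- to 3-fold split between Day 15 and Day 99 areas is a second, separate problem that changing the integration rule does not solve. Neither problem reaches the primary endpoint, which uses RVNA concentrations, response rates and rabies cases. The RVNA AUEC1-15 in SAP 11.3 ends on Day 15, before the gap.

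**What to change.** In SAP 10.3:
1. Replace the linear rule with linear-up/log-down trapezoidal integration for AUC1-t and AUC1-inf. Under the same model the AUC1-t error falls to about -2% to -4%.
2. Add SYN023 AUC1-15 as the common-interval exposure for the NRG and for the LRG-versus-NRG and ADA-status summaries. Days 1, 4, 8 and 15 are scheduled in both groups.
3. Show AUC1-t with its last quantifiable day, and state that NRG CL/F is available only where Day 99 is quantifiable and sampled Cmax is on Day 4.
4. Settle which LRG sampling days apply, since Protocol Table 3-1 and SAP 10.2 differ.

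The cost is one software setting, one added parameter, one extra reporting column and SAP wording; no new samples are needed. AUC1-15 has two limits. It covers only the early part of exposure, so an ADA effect that begins after Day 15 would not show in it. It also inherits the sparse absorption phase: in the worked case 1.37 + 3.45 + 5.10 = 9.92 against an exact 10.75, about 8% low. That shortfall is common to both groups because they share these sampling days.
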